5. OBJECTIVES AND ENDPOINTS

Objectives	Endpoints	Time point(s)
Primary Objective To evaluate prevalence of HRD in our internal cohort of metastatic EGFRm NSCLC	Primary Endpoint Proportion of EGFRm NSCLC with an HRD positive score evaluated by AmoyDx HRD Panel or similar (GSS \geq 50).	At T0 on baseline tumour samples
Secondary Objectives To assess correlations between HRD score (pos/neg) and: 
 - Clinical variables (PFS, OS, metastatic sites) - Molecular events (type of EGFR mutations, VAF, drug resistance mechanisms i.e. gene amplification) 	Secondary Endpoints Overall survival (OS), Progression-free survival (PFS), tumour genomic mutations.	At T0 on baseline tumour samples
Exploratory Objectives 
 - To assess the efficacy of osimertinib and olaparib combination in TKI-naïve EGFRm NSCLC cell lines (HCC-4006, HCC-827, and HCC-2935, ranging from low to high HRD score); - To test the drug combination in patient-derived models of EGFRm tumours (PBMCs, organoids, and PDXs); 	Tumor growth, cellular viability, drug toxicity.	N/A

- To rule out toxicity the drug combination and assess treatment response, thanks to our immune competent GEMM model of EGFRm16 and TP53 wt/null.

6. STUDY DESIGN

The study aims to investigate the prevalence of HRD profiles in advanced EGFR-mutated NSCLC patients. The design is retrospective/prospective observational study, and 100 patients will be enrolled (50 in the retrospective cohort and 50 in the prospective cohort). We plan 4 years of enrollment based on the number of patients with those characteristics accessing at OSR Medical Oncology Unit. Moreover, to calculate clinical parameters such as PFS and OS we plan to follow-up patients for 3 additional years, based on literature survival analysis.

6.1. Study duration

Duration of enrolment: 4 years, starting from ethical approval.

Duration of total study period: 7 years, including 4 years of enrolment and 3 years of follow-up (01/01/2026-31/12/2032). Based on historical caseload at IRCCS Ospedale San Raffaele, we estimate an average of \approx 15 EGFRm metastatic NSCLC patients eligible per year.

Retrospective data collection will include patients respecting the eligibility criteria from 1/1/2020 to 30/09/2025.

7. STUDY POPULATION

7.1. Study Participants

The study population will include adult patients (\geq 18 years) with metastatic EGFR-mutated non-small cell lung cancer (NSCLC). Patients may be included either retrospectively, if already diagnosed and treated with available archival tumor tissue, or prospectively, if newly diagnosed and with tumor samples collected prior to treatment initiation. All participants must have tumor tissue suitable for HRD testing.

7.2. Screening Failures

Screen failures are defined as participants who consent to participate in the clinical study but does not meet the criteria for participation in the study. A minimal set of screen failure information is required to ensure transparent reporting of screen failure participants. Minimal information includes demography, screening failure details, eligibility criteria. Based on the study features, we do not expect a high rate of screening failure.

8. STUDY OBJECT

The object of the study is to evaluate the prevalence of HRD in metastatic EGFRm NSCLC, investigating any correlation with clinical and/or molecular characteristics. As exploratory analysis, the project will assess the combination of Osimertinib and Olaparib in different pre-clinical models, ranging from tumour cell lines to GEMM animal models.

8.1. Study object description

N/A

9. STUDY PROCEDURES

Patients will follow normal clinical practice for advanced EGFR-mutated NSCLC. For the purpose of the study, only data on disease progression/death/survival will be collected, in addition to molecular analysis about HRD on tumor tissue. The flow-chart below is just representative of a normal path of a patient receiving EGFR-TKI in first-line setting, but can be slightly modified according to clinical practice, without any substantial issue.

Legenda: R=for research purposes, C=per clinical practice, *radiological assessments per clinical practice are accepted every 12-16 weeks

	Enrollment	Screening	Baseline	Study Visit	End of Study Visit	Follow-Up Visit
Procedures	Day					
Informed consent	R					
Demographics	C					
Medical history	C		C			
Eligibility assessment		R				
Physical examination (including height and weight)	C		C	C	C	C
Vital signs	C		C	C	C	C
Performance status	C		C	C	C	C
Laboratory test	C		C	C		
Availability of tumor tissue for HRD testing		R				
EGFR-TKI administration			C	C		
Radiologic/Imaging assessment (CT-scan and brain imaging, CT or MRI)	C			C*		
Adverse event				C		

9.1. Informed Consent

Consent forms will be EC-approved, and the participant will be asked to read and review the document. The investigator (according to applicable regulatory requirements) or a person designated by the investigator, and under the investigator's responsibility, will explain the research study to the participant and answer any questions that may arise. A verbal explanation will be provided in terms suited to the participant's comprehension of the purposes, procedures, and potential risks of the study and of their rights as research participants. Participants will have the opportunity to carefully review the written consent form and ask questions prior to signing. The participants should have the opportunity to discuss the study with their family or surrogates or think about it prior to agreeing to participate. The participant MUST sign the informed consent document prior to any procedures being done specifically for the study/any data is collected. Participants must be informed that participation is voluntary and that they may withdraw from the study at any time, without prejudice. A copy of the informed consent document will be given to the participants for their records. The informed consent process will be conducted and documented in the source document (including the date), and the form signed, before the participant undergoes any study-specific procedure and any data is collected. The rights and welfare of the participants will be protected by emphasizing to them that the quality of their medical care will not be adversely affected if they decline to participate in this study.

However, deceased and untraceable patients will also be included. These patients will be pseudo-anonymized according to Institutional procedures. The inclusion of those patients will avoid bias resulting from the exclusion of such subjects (patients selected for outcomes) that could compromise the scientific quality of the study and the purpose of the research. That is, provided the data controller adopts appropriate measures to protect the rights, freedoms and legitimate interests of the individual's data.

9.2. Subject Recruitment and Screening

In this single-center study will be enrolled 100 outpatients affected by advanced EGFR-mutated NSCLC, accessing to Medical Oncology Unit of IRCCS Ospedale San Raffaele. In the retrospective cohort will be enrolled 50 patients, whereas in the prospective cohort we will enroll 50 patients in about 4 years, considering an accrual rate of 15 patients/years. The patients enrolled in the prospective cohort will follow the normal clinical practice, and no additional clinical requirements are needed to be involved in the study. The single parameter that will be investigated in the "screening" phase will be the availability of sufficient tumor tissue to perform HRD analysis.

9.3. Subject Identification

Starting from the signature of the informed consent by the patient or the patient's legal tutor, the subject is considered enrolled in the clinical study. For the retrospective cohort of the study, deceased and untraceable patients will be included as well.

A subject identification code will be assigned consecutively (e.g.: HER_YYY; where HER is the abbreviation of the Protocol Identifier, and YYY is the progressive subject number in increasing order starting from 001).

A patient identification list will be kept.

9.4. Baseline Assessments

Baseline assessment is considered as the visit during which the patient receives EGFR-TKI therapy for the first time (Day 0). This time point will serve as the reference for all subsequent evaluations and will be considered the starting point for survival analyses (Progression-Free Survival and Overall Survival). At baseline, medical history, physical examination (including performance status and vital signs) and routine laboratory data (as per clinical practice) will be recorded.

9.5. Study Visit and Follow Up

For the prospective cohort, study visits will follow routine clinical practice for patients receiving first-line EGFR-TKI.

- Treatment visits: patients will be assessed approximately every month (in accordance with standard clinical practice), including physical examination and vital signs, performance status, adverse event reporting, and laboratory tests as per clinical practice.
- Radiological evaluation: imaging (CT-scan of thorax and abdomen plus brain imaging as per clinical practice) will be performed every 12 to 16 weeks and as per local use.
- Follow-up after treatment discontinuation: patients who discontinue first-line treatment will be followed every 3 months, until death or study end.

The retrospective cohort will be followed from the date of diagnosis/first EGFR-TKI treatment until last available follow-up or death.

All patients (retrospective and prospective) will be followed for survival outcomes up to 3 years after the enrollment of the last patient, consistent with the study design.

9.6. Definition of End of Study

According to the study design, the end of the study is defined as the date on which the last patient completes the last visit (approximately 3 years after the last patient enrollment).

9.7. Premature termination or suspension of a study

As this is an observational, non-interventional study, premature termination or temporary suspension is not expected on the basis of patient safety concerns related to study treatment. However, the study may be suspended or terminated early by the Sponsor or Principal Investigator if deemed necessary.

Circumstances that may warrant early termination or suspension include, but are not limited to:

- inadequate patient recruitment or follow-up;
- data quality concerns, such as incomplete or non-evaluatable data;
- administrative or financial reasons;
- withdrawal of approval by the Ethics Committee or other regulatory authorities.

In such cases, the Sponsor and the Principal Investigator will ensure that appropriate measures are taken to protect participants' interests. Patients already enrolled will continue to receive standard medical care in accordance with institutional clinical practice.

Written notification documenting the reasons for study suspension or termination will be provided by the Sponsor/PI to the Ethics Committee and, if applicable, to participants.

10. DISCONTINUATION AND WITHDRAWAL

Participants are free to withdraw from participation to the study at any time upon request.

The reason for participant discontinuation or withdrawal from the study will be recorded on the clinical records and in the electronic Case Report Form (eCRF). Subjects who sign the informed consent form and subsequently withdraw, or are withdrawn or discontinued from the study, will be replaced.

11. SAMPLE HANDLING

Subject included in the study are patients affected by metastatic EGFRm NSCLC, and diagnostic tissue samples are taken from each participant to the study protocol as part of the standard of care pathway. Archival tumour samples to be used in the study will be those already stored in the Pathology Unit, and tested for HRD status with AmoyDx at the Molecular biology laboratory (in the Pathology Unit). HRD testing costs will be covered by research funding as stated above. No further analysis are planned for this study, and any further and new research will be approved by the EC. The residual material will be stored in the Pathology Unit for 10 years.

12. PATIENT SAFETY

No additional risks are expected for participants, as this is an observational study and all procedures are part of standard clinical practice.

13. DATA MANAGEMENT

13.1. Definition of source data and source documents

Clinical data will be retrieved from patient medical records stored in the electronic medical record system of IRCCS Ospedale San Raffaele (e.g.: “Galileo”, “Xero”). These records serve as the primary source documents and include hospital charts, laboratory results, diagnostic imaging reports, and other relevant clinical information.

Source Data: All information in original records and certified copies of original records of clinical findings, observations, or other activities in a clinical study necessary for the reconstruction and evaluation of the study. Source data are contained in source documents (original records or certified copies). Any data recorded directly on the CRFs (i.e., no prior written or electronic record of data), is considered to be source data.

Source Documents: Original documents, data, and records (e.g., hospital records; clinical and office charts; laboratory notes; memoranda; subjects' diaries or evaluation checklists; pharmacy dispensing records; recorded data from automated instruments; copies or transcriptions certified after verification as being accurate copies, microfiches, photographic negatives, microfilm or magnetic media, x-rays, subject files, or records kept at the pharmacy, at the laboratories, and at medico-technical departments involved in the clinical study).

All parameters asked for in the case report form (CRF) should be documented in the source documents.

A record of patient screen failures will be maintained for patients who do not qualify for enrollment, including the reason for the screen failure.

13.2. Documentation of data in Case Report Forms (CRFs)

Data relevant to the study will be extracted from the source documents and entered into the eCRF CGP (Cohort Genomics Platform). The eCRF can be accessed only to the PI and the involved staff, prohibiting access to unauthorized third parties. CGP is an electronic data capture system specifically developed around HIPAA-Security guidelines.

The creation of eCRFs is done by a team from the Center for Omics Sciences OSR (COSR) in collaboration with Medical Oncology data managers to define the variables and structure. The platform (instance at The OSR clinic servers) is accessed via credentials (with institutional hsr email), account configuration is done by the team itself upon request.

The electronic systems used for data handling and storage are validated and comply with established requirements for completeness, accuracy, reliability, and consistent performance.

A record of patient screen failures will be maintained, including the reason for screen failure, and will also be stored securely.

All parameters required for the CRF will be documented in the source documents.

13.3. Data Recording and Record Keeping

The investigator shall arrange for the retention of Essential Documents for the Conduct of a Clinical study (e.g., patient files, other source data, and the Trial Master File/Investigator Site File) after the completion or discontinuation of the study according to institutional procedures and applicable laws.

13.4. Data Protection

The Investigator (or the Center that will receive the data) undertakes to:

- use the data only for the purposes of the foreseen analyses and within the limits established by the study and approved by the competent EC;
- store data in a secure network system;
- prohibit unauthorised third parties from accessing data, even partially;
- guarantees to limit access to and processing of data only to its employees and collaborators who, upon appointment as an authorized person:
 1. need to process the data in order to carry out their work in relation to the study;
 2. have undertaken to maintain the confidentiality of the Data and of any information deriving from it or that is communicated to them.

If, within the context of the Study, the Investigator (or the Center that will receive the data) needs to make use of its own suppliers, the latter undertakes to appoint these subjects as Data Processors /Responsabili dei Trattamenti with a specific agreement or other legal act suitable for this, before the start of any data processing by them, according to Regulation (EU) n. 2016/679, art. 28.

The Investigator (or the Center that will receive the data) also undertakes to adopt suitable measures to facilitate the exercise of the rights of the subject provided for by Regulation (EU) n. 2016/679, art. 15 – 22, including the rights of access, rectification, cancellation, limitation, opposition and portability, within 30 days of receiving the relative request.

In case the Investigator need to communicate the data outside OSR (the Data Controller /Titolare) in pseudonymized form, the Investigator (or the Center that will receive the data) will refrain from carrying out any activity aimed at identifying the identity of the subjects to whom such data refer. In the event, however, that the data could not be communicated in pseudonymized form by the Data Controller, the Investigator (or the Center that will receive the data) undertakes to adopt all the security and organizational measures aimed at protecting the confidentiality of the Data Subject).

Within 30 days following the end of the study, the Investigator (or the Center that will receive the data) undertakes to cancel the data communicated by the Data Controller or to make them irreversibly anonymous and to promptly communicate it in writing.

A study specific DPIA (Data Protection Impact Assessment), which includes all these aspects and revised by OSR DPO, has been conducted according to applicable data protection law.

14. STATISTICS

14.1. Description of Statistical Methods

The statistical analysis will address the primary, secondary, and exploratory objectives of the study. For descriptive statistics, continuous variables will be summarized using mean, median, range, and standard deviation, while categorical variables will be described using frequency and percentage. Comparisons between groups (e.g., HRD positive vs HRD negative) and time-to-event analyses will be performed with appropriate statistical tests, as detailed in Section 14.4. Statistical significance will be set at a two-sided p-value < 0.05. Analyses will be performed through statistical software such as Microsoft Excel, R, and SPSS.

14.2. Sample Size Determination

According to the literature, the expected prevalence of HRD positivity in NSCLC ranges from 20–30% in early-stage tumours [24]. A similar incidence was observed in a Chinese cohort of any-stage EGFRm or ALK-rearranged NSCLC patients in which the cases with high HRD score are ~33% of the total [18].

Therefore, to obtain an adequate number of patients to allow subgroup analyses and explore clinical and molecular correlations, we calculated a sample size of 100 patients (50 retrospective; 50 prospective) to conduct an exploratory proof-of-concept study, in which we expect to observe around 25 HRD-positive cases (the precision of the estimate corresponds to a 95% confidence interval with a half-width of approximately 8.5 percentage points, which is considered clinically relevant). Based on the historical caseload at IRCCS Ospedale San Raffaele (\approx 15 eligible patients/year), recruiting the planned sample over 4 years is feasible. For the retrospective cohort, we estimate that \approx 30% of patients have insufficient residual archival tumor tissue, therefore the planned 50 patients will be included considering a longer interval (1/1/2020 - 30/09/2025).

14.3. Analysis Populations

The analysis population will include all patients meeting the eligibility criteria, with available tumour tissue suitable for HRD testing. The retrospective cohort will comprise patients already diagnosed and treated with archival tumour tissue available; the prospective cohort will include newly diagnosed patients with tumour samples collected prior to treatment initiation. Patients with insufficient baseline tumour tissue will be excluded from the analyses.

14.4 Statistical Design

For the Primary and Secondary Objectives, continuous variables will be summarized using mean, median, range, and standard deviation. Categorical variables will be described using frequency and percentage. To test association between categorical variables, chi-squared test will be applied. To compare survivals between groups (i.e. HRD positive vs negative, cut-offs to be explored) log-rank test will be applied. Time-to-event outcomes will be represented using Kaplan-Meier curves.

For the Exploratory Objectives, parametric and non-parametric analyses will be used to compare differences in cell lines and phenotypes between groups. For the *in vivo* studies, differences in tumour size and phenotype will be evaluated at different timepoints and compared with t-test. For all statistical tests, $p < 0.05$ will be considered statistically significant.

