Statistical Design	
According to the literature, to obtain an adequate number of patients to allow subgroup analyses and explore clinical and molecular correlations, we calculated a sample size of 100 patients (50 retrospective; 50 prospective) to conduct an exploratory proof-of-concept study, in which we expect to observe around 25 HRD-positive cases (the precision of the estimate corresponds to a 95% confidence interval with a half-width of approximately 8.5 percentage points, which is considered clinically relevant). Based on the historical caseload at IRCCS Ospedale San Raffaele (≈ 15 eligible patients/year), recruiting the planned sample over 4 years is feasible. For the retrospective cohort, we estimate that $\approx 30\%$ of patients have insufficient residual archival tumor tissue, therefore the planned 50 patients will be included considering a longer interval (1/1/2020 - 30/09/2025).
 
For the Primary and Secondary Objectives, continuous variables will be summarized using mean, median, range, and standard deviation. Categorical variables will be described using frequency and percentage. To test association between categorical variables, chi-squared test will be applied. To compare survivals between groups (i.e. HRD positive vs negative, cut-offs to be explored) log-rank test will be applied. Time-to-event outcomes will be represented using Kaplan-Meier curves.
	

	
For the Exploratory Objectives, parametric and non-parametric analyses will be used to compare differences in cell lines and phenotypes between groups. For the in vivo studies, differences in tumour size and phenotype will be evaluated at different timepoints and compared with t-test. For all statistical tests, $p < 0.05$ will be considered statistically significant.
	
Duration of the Study	
Duration of enrolment: 4 years, starting from ethical approval
 
Duration of total study period: 7 years, including 4 years of enrolment and 3 years of follow-up (01/01/2026-31/12/2032). Based on historical caseload at IRCCS Ospedale San Raffaele, we estimate an average of ≈ 15 EGFR^m metastatic NSCLC patients eligible per year.
 
Retrospective data collection will include patients respecting the eligibility criteria from 1/1/2020 to 30/09/2025.
	

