14.5 Potential biases and mitigation strategies

The study is a pilot investigation with a primarily descriptive intent and will include all advanced lung cancer patients with an EGFR mutation treated with TKI inhibitors as standard of care. Retrospective cohort will include patients in the interval indicated (1/1/2020 - 30/09/2025) and those who have received at least one dose of treatment and for whom survival can be estimated (i.e., at least a date of death available). Only patients for whom insufficient archival tumor tissue is available will be excluded, which should not introduce a selection bias. To limit as much as possible bias related to sample size, a prospective cohort has been planned, in order to broaden the study while maintaining its exploratory nature.

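### The survival comparison by HRD status leaves its cut-off open while calling any p < 0.05 significant, although HRD-positive is already defined as GSS ≥ 50

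*Protocol*

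**What the plan says.** Section 5 (and the synopsis) sets the primary endpoint as "Proportion of EGFRm NSCLC with an HRD positive score evaluated by AmoyDx HRD Panel or similar", with the threshold given in brackets as GSS ≥ 50. The secondary objective is "To assess correlations between HRD score (pos/neg) and" clinical variables, which include PFS and OS. Up to this point there is one definition of positive, used for both prevalence and outcome.

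Section 14.4 describes the survival analysis as follows: "To compare survivals between groups (i.e. HRD positive vs negative, cut-offs to be explored) log-rank test will be applied". The synopsis, under Statistical Design, has the same phrase: "HRD positive vs negative, cut-offs to be explored". Section 14.4 closes with "For all statistical tests, $p < 0.05$ will be considered statistically significant", and Section 14.1 makes that threshold two-sided.

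Section 14.2 describes an "exploratory proof-of-concept study, in which we expect to observe around 25 HRD-positive cases" among 100 patients. Section 14.5 adds: "The study is a pilot investigation with a primarily descriptive intent".

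**The concern.** The words about exploring cut-offs are attached to the positive/negative grouping itself, not to a separate sensitivity analysis. A reader cannot tell whether GSS ≥ 50 remains the tested split, whether other splits are tested beside it, or whether one is picked after seeing the data. All three are compatible with the text, and under each of them any p < 0.05 may be called significant.

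Two things are at stake.

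- **Error rate.** A PFS or OS difference by HRD status could be declared significant more than 5% of the time when no association exists. The synopsis hypothesis is that HRD marks a subgroup with prognostic value, so a chance finding here bears directly on what the study sets out to learn.
- **Meaning of the group.** The patients called HRD-positive in the survival result might not be those counted in the prevalence result.

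**Working it through.** **The plan's own figure.** The only computed figure is the precision of the prevalence estimate. With 25 of 100 positive, the half-width is 1.96 × √(0.25 × 0.75 / 100) = 0.0849, or 8.5 percentage points. This reproduces Section 14.2. No power or event count is given for the log-rank tests.

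**Inputs from the protocol.** N = 100 (50 retrospective, 50 prospective); about 25% positive at GSS ≥ 50; two-sided 0.05 for every test; retrospective entry 1/1/2020 to 30/09/2025; four years of prospective enrolment from 01/01/2026; study end 31/12/2032. Potential follow-up is therefore 87–156 months in the retrospective cohort and 36–84 months in the prospective cohort.

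**Assumptions, because the protocol is silent.** The number and position of the cut-offs; that any p < 0.05 counts; exponential survival.

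**Step 1: independence reference.** If the tests were independent, the chance of at least one false positive would be 1 − 0.95² = 9.75% for two and 1 − 0.95³ = 14.3% for three.

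**Step 2: allow for overlap.** Splits of the same score are correlated. For positive fractions p₁ < p₂, the correlation of the two test statistics is √[p₁(1 − p₂) / (p₂(1 − p₁))]. For 25% and 50% this is √[(0.25 × 0.50) / (0.50 × 0.75)] = 0.58. For 25% and 33% it is √[(0.25 × 0.67) / (0.33 × 0.75)] = 0.82. The chance that the largest |Z| exceeds 1.96 was found from 2,000,000 multivariate-normal draws.

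**Step 3: direct check.** Log-rank tests on 20,000 null datasets of 100 patients, with assumed median survival of 36 months and censoring at 36–84 months.

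| Share labelled positive at each cut-off | Normal theory | Log-rank simulation |
|---|---|---|
| 25% only | 5.0% | about 5% |
| 25%, 33% | 7.7% | 7.8% |
| 25%, 50% | 8.8% | 9.2% |
| 25%, 75% | 9.4% | not run |
| 20%, 25%, 33% | 9.7% | 10.2% |
| 25%, 33%, 50% | 10.7% | 11.2% |
| 25%, 50%, 75% | 12.4% | 12.7% |

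**Step 4: the protocol's entry and follow-up pattern.** A further 6,000 null datasets per scenario used the calendar dates above and assumed median OS of 24, 36 or 48 months (censoring 11%, 21% or 30%).

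- One split: 5.1–6.0%.
- Two splits: 8.0–10.0%.
- Three splits: 10.8–14.0%.
- Five splits: 13.9–20.0%.
- Every cut-off between the 25th and 75th percentiles: 27–28%.
- Every cut-off between the 10th and 90th percentiles: 43–44%. This last figure depends on the fineness of the grid; normal theory with 41 cut-offs gives 36%.

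The assumed median hardly changes the results. All figures are per endpoint; testing both PFS and OS adds further multiplicity.

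**Step 5: group mismatch.** GSS ≥ 50 is expected to label about 25 of 100 patients positive. For illustration, a top-third split would label 33 and a median split 50.

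**The case against.** The strongest reply has four parts.

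- **The number of cut-offs and any adjustment belong in the SAP, which is not shown.** It is true that such detail may properly sit there. But the protocol is not simply silent: it states an open split and an unadjusted significance rule, against its own fixed definition. A SAP that tested GSS ≥ 50 alone would depart from this wording.
- **The natural reading is GSS ≥ 50 as the comparison, with other cut-offs beside it.** That reading is possible, and under it the main survival group matches the primary endpoint. The text does not say so, however, and the added splits would still carry p < 0.05 as significant.
- **The study is exploratory and descriptive.** This stands as a limit on severity. The sample size rests on prevalence precision, and no decision rule depends on a survival p-value. It does not remove the problem, because Section 14.4 attaches a significance threshold to every test.
- **The size depends on assumptions.** This also stands. Two neighbouring cut-offs give only about 1.5 times the nominal rate, and three placed close to the expected 25% give about 10%. Part of the excess in simulation, about half a percentage point, is ordinary small-sample behaviour of the log-rank test at a single split. The five-cut-off and scanning figures describe searches that the protocol does not propose, so the conclusion should not rest on them.

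**Conclusion.** The concern holds. The protocol fixes HRD-positive at GSS ≥ 50, reopens that split for PFS and OS, and calls any two-sided p < 0.05 significant. With an assumed two or three cut-offs, and any p < 0.05 counted, the false-positive rate per endpoint is about 7–10% or 10–14% instead of 5%. That is about 1.5 to 2.8 times nominal, for which roughly double is a fair summary. A wider search would be worse. The primary prevalence estimate is not affected. Because only secondary results of a self-described exploratory study are touched, this is a point that should be fixed, not one that undermines the study.

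**What to change.** In Section 14.4 and in the synopsis, make the existing definition the single prespecified split. Suggested wording:

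> *PFS and OS will be compared between HRD-positive (GSS ≥ 50) and HRD-negative patients with the log-rank test. Other cut-offs are hypothesis-generating and will be reported without a p-value or significance claim, or with a p-value adjusted for maximal selection.*

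A Cox model with GSS as a continuous variable could be added to use the whole score, but it is optional.

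The cost is wording in two places. Sample size, data collection and the primary analysis do not change, and other thresholds can still be explored. The one real restriction is that an alternative threshold found in these data could not be called significant without the adjustment or external validation.
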